Eating disorders (EDs) are serious mental illnesses associated with high morbidity and mortality, clinical impairment, and comorbid psychopathology. Although evidence-based treatments for EDs have been established, the treatment gap is wide. Indeed, <20% of individuals with EDs receive treatment. We need a novel solution not only to identify individuals with ED but also to encourage mental health services use and to address treatment barriers. We propose a research agenda to design a conversational agent or "chatbot" that is optimized to increase mental health services use among individuals with EDs through such features as: 1) providing a personalized recommendation for seeking intervention; 2) engaging the user in motivational interviewing to overcome barriers to care; 3) repeated check-ins with the user to encourage follow-up with care; and 4) education on the seriousness and consequences of EDs. Study 2 will utilize a randomized optimization trial with adults who have completed screening on the National Eating Disorders Association (NEDA) website and screen positive for an ED but are not in treatment to determine chatbot feasibility and to generate data on the effect of the chatbot on motivation for treatment and mental health services use at follow ups. This trial will employ the Multiphase Optimization Strategy framework, using a 2⁴ full factorial design, to randomly assign participants to a combination of the three proposed intervention components (n=16 conditions) to isolate the active ingredients. Results from the proposed study will be used to optimize the chatbot, which will then be tested in a subsequent R01 randomized controlled trial.

B2. Primary Hypothesis

We will determine the feasibility of delivering the chatbot and generate data on the effect of the chatbot components on motivation for treatment and mental health services use.

C. Background

C1. Rationale for this Study

Clinical or subclinical EDs impact 10% of individuals in their lifetime, which translates to at least 30 million people in the U.S.¹ Although evidence-based treatments for EDs have been established,² <20% of individuals with EDs receive treatment,³;⁴ which is problematic given that lack of or delays in treatment result in poorer prognosis and greater relapse.⁵ While few individuals with an ED receive treatment specifically for their disorder, these individuals exhibit elevated health services use and costs compared to those without an ED.⁶ The problem of access to care for EDs is even worse amongst racial/ethnic minority individuals.⁻¹¹ Receiving services for a psychiatric disorder involves multiple steps, with identifying or learning one's symptoms are something in need of help being a crucial first step.⁴ Yet even once symptoms are identified, individuals with EDs may experience numerous barriers to care, including stigma, denial of illness severity, lack of knowledge about resources, and practical barriers such as cost.¹¹⁰ We need a novel solution to not only identify individuals with EDs but to also encourage mental health services use and address treatment barriers.

C2. Prior Literature and Studies

A conversational agent or "chatbot" has great potential for increasing mental health services use among those with EDs. People respond psychologically to chatbots as if they are people, even when they are aware they are conversing with a robot. ^{11;12} In one study, when people talked to an automated chatbot, they were less fearful of self-disclosure and displayed more intense sadness compared to those who thought the chatbot was human-controlled. ¹³ There is optimism regarding a role for chatbots in mental health; ^{11;14} the scalability, cost-effectiveness, and anonymity they provide make them ideal for delivering mental health interventions.

Pilot work has demonstrated chatbots may be capable of instigating change in symptoms and behaviors related to health and mental health. College students with depression and anxiety who were assigned to a chatbot that delivered cognitive-behavioral therapy (CBT) self-help content reduced their depression over the course of 3 weeks, more so than the control. Chatbots have also demonstrated success with promoting medication adherence for individuals with schizophrenia over 1 month. Another study demonstrated sustained activity levels in overweight individuals when provided with a chatbot that set goals and gave personalized feedback, compared with a decline in activity in the control. Overall, a 2017 scoping review identified 49 studies on conversational agents; none addressed EDs. The review concluded that most studies show good usability and acceptability but that more research on clinical effectiveness is needed.

In order to be successful, our novel chatbot would require the following features. First, we would need the capability to provide easily accessible ED screening that would allow for the identification of large numbers of individuals with EDs. Currently, many ED cases go undetected. A majority of individuals who ultimately receive treatment for an ED are first seen by their primary care physician, but 92% of these providers believe they have missed ED diagnoses.¹⁹ This highlights the need for widely available online ED screening. Second, we would need the capability to provide personalized recommendations for seeking intervention while taking into account participant characteristics and addressing treatment barriers. Research has demonstrated that among college students at elevated risk for suicide, completion of an online mental health screen, accompanied by personalized feedback and the option to engage in brief online motivational interviewing (MI)-based counseling to address treatment barriers ("eBridge"), resulted in greater treatment readiness and linkage with treatment versus screen feedback only.²⁰ Relatedly, recent work with a number of patient populations (e.g., autism, severe mental illness) has demonstrated success with "navigator models" whereby a health care professional or paraprofessional assists patients in navigating health care systems and in overcoming gaps in service delivery. 21-24 A current NIMH initiative encourages research in this area (PAR-18-428) as a potential solution to the wide treatment gap for psychiatric disorders.²⁵ Third, the solution needs to be scalable to large user populations, for which mobile approaches hold great promise.²⁶ Although in-person navigator models have demonstrated some success in increasing services use, ²¹⁻²⁴ high labor costs limit scalability.

There are very promising preliminary data on mental health chatbots built by X2AI, our chatbot design collaborator for this study. In one study, those with access to "Tess," X2AI's chatbot designed to target depression and anxiety using CBT, experienced reductions in depression and anxiety over 2-4 weeks with a d=.68 reported for depression.²⁷ One large health system in the U.S. customized X2AI's chatbot to deliver interventions based on MI and behavioral activation to

reinforce weight management goals in adolescents with pre-diabetes, with users rating the chatbot useful 96% of the time. ²⁸ Third, our group has begun work with X2AI to develop a chatbot called "Tessa" to serve as an automated moderator for our well-established indicated ED prevention program, StudentBodies. ²⁹⁻³¹ While still in development, preliminary user feedback has been very positive.

Research has shown support for the components proposed for inclusion in the chatbot: 1) meta-analytic findings have indicated that tailored messages have a greater impact on health behavior than control $(r=.074)^{32}$ and that text message based health promotion messages have an effect of d=.33, with greater efficacy for those using personalization (p=.001);³³ 2) a review of meta-analytic findings found that MI is significantly more effective than no treatment (ds up to .57) for a wide variety of problems and increasing treatment engagement;^{34;35} 3) meta-analytic findings have indicated that reminder systems improve medication adherence in chronic disease $(d=.41)^{36}$ and other issues;³⁷ and 4) a meta-analytic study found psychoeducation to reduce symptoms of depression and psychological distress $(d=.2)^{38}$.

D. Study Objectives

D1. Study Aim

Aim 1) To determine chatbot feasibility and to generate preliminary data on the effects of the chatbot components on motivation for treatment and services use, employing the MOST framework. Aim 2) To test whether the chatbot components interact to predict outcomes.

Data will inform the development of an optimized chatbot, which I will test in an ensuing R01 randomized controlled trial.

D2. Rationale for the Selection of Outcome Measures

The goal is to determine the feasibility of delivering the chatbot and to generate data on the effect of the chatbot components on motivation for treatment and mental health services use. Motivation for treatment and mental health services use are the two main outcomes that will provide data for which chatbot components are most efficacious in promoting help seeking behaviors. We will also explore if the chatbot components interact to predict outcomes, which will also inform an optimized chatbot to be tested in a subsequent R01 trial.

E. Study Design

E1. Overview or Design Summary

We have used a user-centered design approach to create a single chatbot prototype, which includes four key features: 1) providing a personalized recommendation for seeking intervention; 2) engaging the user in motivational interviewing to overcome barriers to care; 3) education on the seriousness and health consequences of eating disorders; and 4) repeated check-ins with the user to encourage follow-up with care.

Study 2 will use a 2⁴ full factorial trial design to test the four binary chatbot components. Thus, there are 16 experimental conditions, and participants will be randomized to 1 of those 16

conditions. Participants can be assigned to intervention ("yes") or control ("no") conditions for each chatbot component.

Participants will be recruited from those who complete the NEDA online screen and who meet eligibility criteria of screening positive for a clinical/subclinical ED, at least 18 years old, and not currently in treatment for an ED. For a period of time on the NEDA site, eligible users will be offered the chatbot. Interested individuals will be taken to a Qualtrics screen wherein those who endorse owning a smartphone and being a U.S. resident will be given access to participate in our study. Data from the NEDA eligibility screen will be collected. The consent form will be shown via Qualtrics and will encourage interested individuals to call a member of our research team to discuss the study. Once a participant completes the baseline measures, they will be randomized using Qualtrics. Once the baseline measures are completed, participants will be given information on how to access the chatbot and their unique chatbot start code.

Participants will engage with the chatbot for between 5-20 minutes, dependent on condition. Participants who are randomized to the repeated administration module will complete approximately 3 new conversations over the course of 2 weeks. The chatbot will automatically reach out to a participant if they do not complete a conversation within 1 day.

Assessments will occur online and may include data from the initial ED screen completed on the NEDA website. Assessments will take place at baseline (i.e., prior to chatbot use), and at approximately 2, 6, and 14 weeks after baseline completion via Qualtrics (see *F.2 Schedule of Measurements*).

We will document recruitment rates (i.e., percent of those offered participation in the study who sign up), as well as study retention rates, to assess appropriateness of follow-up procedures. Demand for the chatbot will be measured as: 1) number of texts to the chatbot; and 2) engagement at repeated administrations (if randomly assigned to this condition).

To validate receipt of treatment, a study team member will contact a random subset of participants (i.e., approximately 10%) who reported engaging in some kind of treatment to solicit additional details on their service use and experience through phone/Zoom call or online questionnaire, which will provide additional validation, and when possible, participants will also be asked to provide some kind of documentation for the services they reported using (e.g., send receipt of therapy session or provide email indicating they signed up for a recommended online program).

Participants will receive invitation and reminders via email, phone, and/or text message for each assessment, and if they have not completed the conversation with the chatbot. Participants may receive thank you messages for completing assessments.

PHI discussions via email will use WashU guidelines: 1) a test email will be sent to the participant to verify their identify (confirm correct recipient) and that this email will be sent in a secure manner (i.e., [secure] in subject line); 2) The body of the email will instruct the participant to send all information as a response to this thread and to not remove the "[secure]" from the subject line; 3) document in our research records the participant's agreement to provide information over email.

E2. Subject Selection and Withdrawal

E2.A. Inclusion Criteria

U.S. resident; English-speaking; age 18 years or older; own a smartphone; screen positive for a DSM-5 clinical or subclinical eating disorder; not receiving treatment for an eating disorder

E2.B. Exclusion Criteria

We will exclude participants who are currently receiving treatment for an eating disorder given the goal to increase access to services for those not receiving help. In addition, we do not plan on enrolling individuals who screen for Avoidant Restrictive Food Intake Disorder.

E2.C. Ethical Considerations

All key personnel involved in the design or conduct of research involving human subjects will receive the required education on the protection of human research participants prior to the start of the study. Participants will be informed that they do not have to answer any questions that make them uncomfortable. There are minimal risks for participating in testing.

Participants will be provided with the contact information of the research staff. As a clinical psychologist, the PI is trained in how to address safety issues. If any participant appears to be in crisis, they will be given information to call emergency services and will be notified that the chatbot is not designed to provide crisis support. Any adverse event will be reported promptly to the mentorship team, the NIH, and the IRB.

Confidentiality: Participant confidentiality will be maintained in compliance with HIPAA privacy protected servers. Study IDs will be linked with participant names, email addresses, and phone numbers in a separate password-protected file stored on a secure, password-protected server that only key study personnel have access to. All employees of the study with access to protected health information (PHI) are required to complete HIPAA training and comply with the privacy procedures in place at Washington University.

X2AI (x2ai.com), our chatbot collaborator, is a HIPAA-compliant mental health chatbot company with a dedicated and talented team of software engineers who are experienced in building chatbots that support mental health. X2AI will host the proposed chatbot and all data collected within the chatbot. X2AI will comply with the rules regarding handling of PHI under HIPAA.

Adverse Events: For the purpose of this study, adverse events will be defined as unanticipated problems involving risks to the study participants. A serious adverse event will be defined as any untoward occurrence that results in death, is life-threatening, or creates persistent and significant disability. The PI will consult with mentors to identify serious adverse events. Any potentially adverse events will be evaluated by the PI within 72 hours. All serious adverse events will be immediately reported to the IRB. All adverse events and study withdrawals, together with a detailed explanation of the event and withdrawal, will be provided to the mentorship team.

It is important to note that in previous similar clinical trials of digital health interventions, the procedures outlined above have been used to protect against and minimize potential risks to

participants, and they have proved effective in preventing emotional and physical complaints as well as adverse events.

E2.D. Participant Recruitment Plans and Consent Process

We plan to enroll approximately 200 English-speaking adults ≥18 years with a DSM-5 clinical or subclinical eating disorder who own a smartphone and are not in treatment for an eating disorder.

Participants will be recruited from the NEDA online screen. Once an individual screens positive for a clinical/subclinical ED, is not currently in treatment, and is ≥18 years old, they will be given a link to the Qualtrics eligibility screen. If an individual endorses owning a smartphone and being a U.S. resident, they will be shown the consent form in Qualtrics and will be asked to either agree to or decline participation in the study. Individuals will be encouraged to call a member of our research team to discuss the study.

E2.E. Randomization Method

Study 2 will use a 2⁴ full factorial trial design to test the four binary chatbot components: psychoeducation, motivational interviewing, personalized recommendations, and repeated administration. Thus, there are 16 experimental conditions, and participants will be randomized to 1 of those 16 conditions. Participants can be assigned to intervention ("yes") or control ("no") conditions for each chatbot component.

Risks

There are minimal risks for participants.

Physical Risks: N/A

Psychological Risks: Our proposed chatbot designed to facilitate mental health problems may promote increased focus on mental health symptoms in some individuals. It is also possible that participants may feel uncomfortable disclosing information about certain behaviors such as disordered eating. However, we have asked questions of a similar nature in several studies in the past and have not had participants report discomfort.

Social Risks: There may be some embarrassment related to completing questions related to disordered eating symptoms.

Financial Risks: N/A

Legal Risks: N/A

Risks to Privacy: We will go to great lengths to keep participant information private and confidential. Participant confidentiality will be maintained in compliance with HIPAA regulations.

Other Risks: N/A

Alternative Treatments: N/A -- Participants in the current study will be participating in usability testing to inform the development of a chatbot for facilitating mental health services use in individuals with eating disorders not currently in treatment. The proposed chatbot is designed to increase the likelihood that individuals will seek mental health care. There are no other widely available digital tools designed for this purpose. All participants who participate in the usability testing will be offered referral information for in-person/ telehealth treatment.

Benefits

The benefits to participants in this study and to society are expected to be great. In terms of possible benefits to participants, they include potential improved uptake of services. In addition, if successful, this study could demonstrate the potential of utilizing a chatbot to bridge the treatment gap for individuals with eating disorders by connecting them to treatment. Therefore, the potential risks that are associated with this study are reasonable when considering the many benefits that participants and society may gain.

Importance of the Knowledge to be Gained: Eating disorders are serious mental illnesses associated with high morbidity and mortality, clinical impairment, and comorbid psychopathology. Although evidence-based treatments for eating disorders have been established, the treatment gap is wide. Indeed, <20% of individuals with eating disorders receive treatment, which is problematic given that lack of or delays in treatment result in prolonged illness, poorer prognosis, and greater likelihood of relapse. Thus, developing a scalable, digital intervention to address this wide treatment gap is crucial. Furthermore, applying user-centered design and usability testing will result in a chatbot that aligns with users' needs, which may increase engagement and improve outcomes. Once established, the proposed chatbot has the potential to be a scalable tool that can facilitate mental health services use for individuals with eating disorders and also has great potential to be applied for use with other psychiatric disorders as well.

E2.G. Early Withdrawal of Subjects

Informed consent will make clear that participants may withdraw at any time with no penalty.

E2.H. When and How to Withdraw Participants

Taking part in this research study is voluntary. Participants may choose not to take part in this research study or may withdraw their consent at any time. They may withdraw by telling the research team they are no longer interested in participating in the study or they may send in a withdrawal letter. There will be no penalty or loss of benefits to which they were otherwise entitled.

E2.I. Data Collection and Follow-up for Withdrawn Subjects

When a participant withdraws from the study, the research team will stop collecting data from them.

F. Study Procedures

F1. Screening for Eligibility

Eligibility will be assessed using the NEDA eating disorder screen and eligibility questions in Qualtrics.

F2. Schedule of Measurements

Measure	NEDA Screen	Baseline Assessment	Chatbot Use	2 Week	6 Week	14 Week	Explanation/ Primary Purpose
SWED	X						To determine if the individual has a clinical/subclinical ED and to determine if they are in treatment.
Demographic Questions	x	Х					To determine if individuals are 18 years or older. To obtain demographic information for analyses.
Recruitment Rates	Х	Х					To obtain the percentage of those offered participation who enroll.
Retention Rates				X	Х	x	To obtain the percentage of follow-up completion.
Demand for Chatbot			X				Number of texts sent to the chatbot and engagement with repeated administration, if applicable.
SUS and USE				Х	Х		To examine usability of the chatbot.

Target measure: motivation for treatment and mental health services use questions	х	Х	х	х	To determine motivation for treatment and mental health services use.
Target measure: SE- KNOW	Х	Х	x	x	To determine self- efficacy in help seeking.
Target measure: personal relevance question	Х	Х	Х	х	To determine efficacy of personalized recommendation component.
Target measure: Dissonance Thermometer	Х	X	x		To determine efficacy of motivational interviewing component.
Target measure: opportunity question	X	х	Х	Х	To determine efficacy of repeated administration component.
Target measure: EDs Literacy Scale	Х	X	×	Х	To determine efficacy of psychoeducation component.
EDE-Q	Х		Х	Х	To examine ED symptoms.
EDs Quality of Life Scale	Х		Х	Х	To examine quality of life.
Patient Health Questionnaire 9	Х		х	Х	To examine depression.
Generalized Anxiety Disorder 7	Х		Х	Х	To examine anxiety.
Treatment and Barriers to Care Questions	Х		X (if no to receiving treatme nt)	X (if no to receivin g treatme	To determine any barriers to treatment utilization.

l					
ı				nt)	
ı					

F3. Data Collection and Reporting Procedures for Adverse Events

For the purpose of this study, adverse events will be defined as unanticipated problems involving risks to the study participants. A serious adverse event will be defined as any untoward occurrence that results in death, is life-threatening, or creates persistent and significant disability. The PI will consult with mentors to identify serious adverse events. Any potentially adverse events will be evaluated by the PI within 72 hours. All serious adverse events will be immediately reported to the IRB. All adverse events and study withdrawals, together with a detailed explanation of the event and withdrawal, will be provided to the mentorship team.

F4. Study Outcome Measurements and Ascertainment

The goal is to determine the feasibility of delivering the chatbot and to generate data on the effect of the chatbot components on motivation for treatment and mental health services use. We will also explore if the chatbot components interact to predict outcomes. Data will inform developing an optimized chatbot, which we will test in a subsequent R01 trial.

The goal of this optimization trial is to inform an R01 randomized controlled trial of an optimized chatbot vs. a control condition. We will achieve that goal by evaluating feasibility and generating effect sizes of each component on outcomes, which will inform which components to retain in the optimized chatbot and be used to power a subsequent R01 trial.

G. Data Handling and Record Keeping

G1. Confidentiality and Security

Participant confidentiality will be maintained in compliance with HIPAA privacy protected servers. Study IDs will be linked with participant names and email addresses in a separate password-protected file stored on a secure, password-protected server that only key study personnel have access to. All employees of the study with access to protected health information (PHI) are required to complete HIPAA training and comply with the privacy procedures in place at Washington University.

X2AI (x2ai.com) is a HIPAA-compliant mental health chatbot company with a dedicated and talented team of software engineers who are experienced with building chatbots focused on supporting mental health. X2AI will host the proposed chatbot and all data collected within the chatbot. X2AI and Washington University are in a Business Associate agreement. X2AI will comply with the rules on handling of PHI under HIPAA.

Training: All staff personnel are trained and comply with HIPAA regulations. All study team members will complete the CITI training and Good Clinical Practice training.

Performance Monitoring: The Data and Safety Monitoring Plan for this trial includes close monitoring by the PI and her mentoring team. Any adverse event will be reported promptly to the NIH and to the IRB.

H. Study Administration

H.1. Funding Source and Conflicts of Interest

This study is funded by NIH. Any potential financial conflicts of interest for individual research team members are reported according to the IRB requirements and procedures.

H.2. Participant Payment

Participants will receive a \$5 electronic gift card for completion of the baseline assessment, a \$10 electronic gift card for completion of the 2 week assessment, a \$10 electronic gift card for completion of the 6 week assessment, and a \$20 electronic gift card for completion of the 14 week assessment.

H.3. Study Timeline

As detailed in the table below, recruitment and enrollment for the randomized pilot trial (Study 2) will begin in the middle of Year 2. It is anticipated that enrollment will continue for one year, into the middle of Year 3. All enrolled participants will receive access to chatbot designed to facilitate health care utilization. Engagement with the chatbot will occur for up to approximately 2 weeks. Participants will complete a baseline assessment, and follow up assessments about 2 weeks, 6 weeks, and 14 weeks after baseline completion.

		Year 1		Year 2		Year 3		Year 4	
Study	Activity	1-	7-	13-	19-	25-	31-	37-	43-
		6	12	18	24	30	36	42	48
	Recruit and enroll participants				X	X			
Study 2:	Deliver the chatbot				X	X			
Randomized Optimization	Conduct follow-up assessments				X	Х	Х		
Trial	Analyze data and write-up						X	Х	
	Write and submit NIH R01 grant					Х	Х	X	X

I. References

- 2. Hay P. A systematic review of evidence for psychological treatments in eating disorders: 2005-2012. Int J Eat Disord. 2013;46(5):462-9. PMID: 23658093.

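### The protocol describes no way to end chatbot contact while staying in the 2-, 6- and 14-week assessments; the one exit it describes ends all further data collection

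*Combined protocol and SAP*

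**What the plan says.** **Exit.** Protocol E2.H treats withdrawal as leaving the study or withdrawing consent: "They may withdraw by telling the research team they are no longer interested in participating in the study", or by letter. There is no penalty. E2.I gives the consequence: "When a participant withdraws from the study, the research team will stop collecting data from them". No exception is written for safety or for services use.

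**Contact.** E1 describes active outreach: "The chatbot will automatically reach out to a participant if they do not complete a conversation within 1 day". It adds: "Participants will receive invitation and reminders via email, phone, and/or text message for each assessment, and if they have not completed the conversation". Participants randomised to repeated administration also have about 3 new conversations over 2 weeks. H.3 puts chatbot engagement at up to about 2 weeks.

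**Explanation of withdrawals.** E2.C and F3 carry the same sentence: "All adverse events and study withdrawals, together with a detailed explanation of the event and withdrawal, will be provided to the mentorship team".

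**Foreseen risk.** The Risks text under E2.E says that the chatbot "may promote increased focus on mental health symptoms in some individuals".

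**Analysis.** The SAP handles censoring and missing data by maximum likelihood in the services-use model, and missing data likewise in the help-seeking attitudes model. It states no sensitivity analysis for withdrawals.

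**The concern.** Two different decisions share one exit. A participant may want the messages to stop, or may want to give no more data. In the available text only the second has a procedure. A participant who uses it to achieve the first also drops out of online assessments that they might have been willing to complete.

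Three things make this matter here. Contact is part of what is randomised: repeated administration adds conversations, so the motive to leave could be stronger at one level of that component than at the other. The lost data include a primary outcome, services use at 2, 6 and 14 weeks. And under F4 the component effect sizes decide which components are retained and are used to power the next trial, so a differential loss would carry forward into both decisions.

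There is also a smaller procedural gap. The mentorship team is to receive a detailed explanation of each withdrawal, but no section says that anyone asks for the reason, when, or how. A letter, or a statement that the participant is no longer interested, need not contain one.

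**Working it through.** The documents give no withdrawal rate and no power calculation behind the enrolment of about 200, so there is no planned figure to reproduce. The check is of the text, followed by an illustration of scale.

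**Step 1. What each kind of participant contributes.**

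- *Ignores the chatbot but does not withdraw.* Under E1, assessment invitations and reminders continue, so all three follow-ups remain scheduled.
- *Withdraws before week 2.* Services use is asked at baseline, 2, 6 and 14 weeks (F2), so there is no post-baseline report. As the F2 table reads, the EDE-Q, PHQ-9 and GAD-7 are taken at baseline, 6 and 14 weeks, so only baseline scores exist.
- *Withdraws between weeks 2 and 6.* The 2-week services-use report may exist, but later reports do not. There is still no post-baseline symptom score.

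Chatbot engagement ends at about 2 weeks, before the first post-baseline symptom measurement. Anyone who leaves during exposure therefore has no post-baseline symptom score.

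**Step 2. Effect on a component's odds ratio.** All inputs are assumed. True 14-week services use is 20% at both levels of a component (odds ratio 1.0). A fraction w withdraws before week 2, and a fraction q of withdrawers would have sought care. The rate seen among those who stay is

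observed = (0.20 − w × q) / (1 − w).

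- w = 10% vs 5%, q = 5%: 0.195/0.90 = 21.67% and 0.1975/0.95 = 20.79%. Odds ratio 0.2766/0.2625 = 1.05.
- w = 20% vs 5%, q = 0: 0.20/0.80 = 25.0% and 0.20/0.95 = 21.05%. Odds ratio 0.3333/0.2667 = 1.25.
- w = 20% vs 5%, q = 40%: 0.12/0.80 = 15.0% and 0.18/0.95 = 18.9%. Odds ratio 0.1765/0.2338 = 0.75.

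The direction depends on whether withdrawers would have sought care less or more often than the 20% assumed overall. The documents do not settle that.

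**Step 3. Sampling error for comparison.** Take 100 per level (about 200 enrolled and equal allocation, the latter assumed). The second case is then 20 of 80 against 20 of 95. The standard error of the log odds ratio is √(1/20 + 1/60 + 1/20 + 1/75) = √0.13 = 0.361, which gives a 95% interval of about 0.62 to 2.53 around 1.25.

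**Step 4. Bounds without an assumption on q.** For a risk difference, counting all withdrawers first as users and then as non-users gives bounds of width w1 + w0, the sum of the two withdrawal fractions. With equal observed rates:

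- 5% withdrawal at each level: −5 to +5 points
- 10% at each level: −10 to +10 points
- 20% at each level: −20 to +20 points

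**Step 5. Power.** For d = .33 (the text-messaging effect cited in C2), 100 per level and two-sided alpha 0.05, power is 64.6% with no loss, 62.3% at 5%, 60.0% at 10% and 55.1% at 20%. At low withdrawal the power cost is modest; the larger issue is possible bias.

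**Step 6. E2.I against E2.C and F3.** E2.I applies once a participant has withdrawn. E2.C and F3 ask for an explanation of the withdrawal. Under E2.H the participant contacts the team in order to leave, so a reason can be noted at that contact. The sections can all be followed as written; what is missing is the step that obtains the reason.

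**The case against.** The strongest reply is that stopping data collection when consent is withdrawn is ordinary protection of participants, not an error. That stands, and the fix keeps it.

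It can also be said that no section forbids asking staff to stop the messages, that staff contact details are provided, and that exposure lasts only about 2 weeks. The consent form, where opt-out wording might sit, is not in the review copy. This limits the point to the text available, but it does not supply a procedure in E2.H or E2.I, where one would be expected.

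A reader might infer several stronger things that the documents do not support:

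- *That E2.I contradicts the duty to explain withdrawals.* It does not, because the reason can be recorded at the withdrawal contact.
- *That withdrawers leave with no data at all.* Baseline scores exist, and nothing says that data already collected are discarded.
- *That anyone who stops using the chatbot is lost.* E1 keeps such people on the assessment schedule.
- *That distress drives withdrawal and is hidden.* The Risks text names increased focus on symptoms as a possible effect but does not link it to withdrawal. Withdrawals go to the mentorship team, and retention and chatbot engagement are documented. What is not written is reporting of withdrawals by component.
- *That the bias favours the component with more contact.* Step 2 gives odds ratios on both sides of 1.0.

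**Conclusion.** The point holds as a gap in design, not as a contradiction. In the available text, E2.H describes only leaving the whole study, E2.I then ends all further data collection, and no route is described for ending chatbot contact while staying in the assessments. A participant who leaves to stop the messages gives no further services-use data and, if this happens in the first 2 weeks, no post-baseline symptom scores.

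Because contact intensity differs by randomised component, the loss could differ by component and bias its effect. The size and direction are unknown. The illustrative odds ratios of 0.75, 1.05 and 1.25 against a true 1.0 rest wholly on assumed withdrawal and care-seeking rates, and even 1.25 lies well within the sampling error of a trial of this size. They show that the loss can matter, not that it will. The change is still worth making, because it is cheap and the lost data bear on a primary outcome and on which components are retained.

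**What to change.** In E2.H and E2.I, separate two requests:

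- (a) A participant's request to end chatbot contact and chatbot reminders, with an offer to remain in the online assessments.
- (b) Withdrawal from all further data collection, which stays free of penalty.

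At either step ask one optional question on the reason, with distress and too many messages among the answers. This gives the explanation required by E2.C and F3 a defined source. Report counts and reasons for (a) and (b) by component.

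The cost is a minor amendment to the protocol and consent form plus one optional question, with no extra visits or staff. If the consent form already contains such a choice, E2.H and E2.I need only be brought into line with it.
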